1.2. Schema

1.3. Schedule of Activities (SoA)

Period I - Optional Prescreening: The study includes an optional prescreening visit (Visit 601) as a simple way for sites to determine whether participants meet Lp(a) criteria, as assessed by a central laboratory assessment, before the full screening activities are initiated at Visit 1. If the participant has not had Lp(a) measured before or is unknown, the prescreening visit should be completed. The prescreening visit can be conducted at the study site, or remotely, for example, at a mobile healthcare or alternate laboratory. The prescreening activities will be described in an appropriate informed consent form (ICF). Informed consent for the prescreening activities will be obtained, a participant identification number will be assigned, and sample for the Lp(a) prescreening laboratory test will be obtained. The optional prescreening visit can be repeated 1 time (no more) per participant if the investigator believes the participant would meet criteria at a later time, with a minimum of 4 weeks between visits. Repeated sampling in the prescreening is opted for, central laboratory testing for Lp(a) is still required as part of the screening procedures conducted at Visit 1. Participants with Lp(a) <175 nmol/L at Visit 1 will not be eligible for enrollment, despite their values in prescreening. A prescreening visit occurring longer or shorter than 21 days (3 weeks) from screening will not be considered a protocol deviation.

Period II - Screening: Visit 1 procedures may be conducted over more than 1 day as long as all activities are completed prior to Visit 2.

Period III - Treatment and Assessment Period: All procedures (screening and baseline) need to be completed prior to the first dose of study intervention. For an early discontinuation (ED) from the study intervention that occurs before the last visit in treatment period, see the activities listed for ED in this table.

	Period I - Pre- Screening	Period II - Screening			Per	riod I	II T	reatm		Participants are required to fast before Visits 1-12. See Section 5.3.1. If a participant arrives not fasted, schedule the laboratory draw for another date.					
Visit number	601	1	2	3	4	5	6	7	8	9	10	11	12	ED	
Days from randomization	≤42	≤21		15	30	60	120	180	210	240	300	360	540		Visit 1 procedures may be conducted over more than 1 day if all activities are completed within the allowable visit tolerance.

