	Period I - Pre- Screening	Period II - Screening			Per	riod I	II T	reatm	Participants are required to fast before Visits 1-12. See Section 5.3.1. If a participant arrives not fasted, schedule the laboratory draw for another date.						
Visit number	601	1	2	3	4	5	6	7	8	9	10	11	12	ED	
Days from randomization	≤42	≤21		15	30	60	120	180	210	240	300	360	540		Visit 1 procedures may be conducted over more than 1 day if all activities are completed within the allowable visit tolerance.
Visit interval tolerance (days)	See Section 1.3	—		±3	±3	±3	±7	±7	±7	±7	±7	±7	±14		
Vital signs		Х	x	X	X	Х	х	х	х	х	х	х	х	х	Includes pulse rate and blood pressure measured after participant has been sitting at least 5 minutes and before ECG tracing and collection of blood samples for laboratory testing.
Physical examination		Х											х	Х	The physical examination is performed (excludes pelvic, rectal, and breast examinations unless clinically indicated).
Symptom- directed physical assessment								Х							Symptom-directed physical assessment will be conducted at the discretion of the PI or qualified personnel, per local regulations, as indicated based on participant status and standard of care.
12-Lead ECG (local)		Х						X				X	X	X	Collect single, local ECG prior to collection of blood samples for laboratory testing, including PK samples. Participants should be supine for approximately 5 to 10 minutes before ECG collections and remain supine but awake during the ECG collection. ECGs may be repeated at the PI's discretion at any visit. See Section 8.2.1.

	Period I - Pre- Screening	Period II - Screening			Pei	riod I	11 T	reatmo		Participants are required to fast before Visits 1-12. See Section 5.3.1. If a participant arrives not fasted, schedule the laboratory draw for another date.					
Visit number	601	1	2	3	4	5	6	7	8	9	10	11	12	ED	
Days from randomization	≤42	≤21	_	15	30	60	120	180	210	240	300	360	540		Visit 1 procedures may be conducted over more than 1 day if all activities are completed within the allowable visit tolerance.
Visit interval tolerance (days)	See Section 1.3			±3	±3	±3	±7	±7	±7	±7	±7	±7	±14		
Laboratory Tests and Sample Collections															
Hematology		Х			Х	Х		Х	Х	Х		Х	Х		
Clinical chemistry		Х	Х	Х	Х	Х		Х	Х	Х		Х	Х	Х	
Lipid panel		Х	Х			Х		Х		Х		Х	Х	Х	
Urinalysis		Х				Х		Х		Х		Х	Х	Х	
UACR		Х				Х		Х		Х		Х	Х	Х	
Serum pregnancy		Х													Females only.
FSH		Х													Optional; performed as needed to confirm postmenopausal status. See Appendix 10.4.

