5.1. Inclusion Criteria

Participants are eligible to be included in the study only if all of the following criteria apply:

Age

1. Participants must be at least 40 years old at the time of signing the informed consent.

Type of Participant and Disease Characteristics

- 2. Participants with $Lp(a) \ge 175$ nmol/L at Visit 1, measured at the central laboratory.
- 3. Participants on the following medications according to local practice must be on a stable regimen for at least 4 weeks prior to Visit 1 and expected to remain on a stable regimen through the end of the Treatment and Assessment Period:
 - a. lipid-lowering drugs (such as statins, ezetimibe, PCSK9 inhibitors, prescriptiondose niacin, fibrates, fish oil, or other products containing omega-3 fatty acids, including over-the-counter [OTC] preparations)
 - b. testosterone, estrogens, anti-estrogens, progestins, selective estrogen receptor modulators, or growth hormone

Weight

4. Have a body mass index within the range 18.5 to 40 kg/m^2 , inclusive.

Sex and Contraceptive/Barrier Requirements

- 5. Male and/or female
 - a. Males who agree to use highly effective/effective methods of contraception may participate in this trial.
 - b. Women of childbearing potential (WOCBP) are excluded from the trial.
 - c. Women not of childbearing potential (WNOCBP) may participate in this trial.

Please refer to Appendix 10.4 for definitions and additional guidance related to contraception.

Contraceptive use by participants should be consistent with local regulations regarding the methods of contraception for those participating in clinical studies. For the contraception requirements of this protocol, see Appendix 10.4.

Informed Consent

6. Capable of giving signed informed consent as described in Appendix 1 (Section 10.1), which includes compliance with the requirements and restrictions listed in the informed consent form (ICF) and in this protocol.

Other Inclusions

7. Are reliable and willing to make themselves available for the duration of the study and are willing to follow study procedures, in the opinion of the investigator.

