#### 9.3.3. Secondary Endpoint(s)/Estimand(s) Analysis

Secondary endpoints are listed in Section 3.

The efficacy analyses for the secondary endpoints will use the FAS described in Section 9.3.1. and may also pool the two LY3819469 400-mg treatment groups, where appropriate.

Analyses for percent change from baseline in time-averaged Lp(a) over Days 240-360 will be conducted in a manner similar to the primary efficacy analysis discussed in Section 9.3.2.

The continuous clinical measures, including Lp(a), ApoB, and hsCRP, may be log transformed before statistical analyses, if deemed necessary. Analyses for change from baseline in each log-transformed parameter at Days 60, 180, 240, 360, and 540 will be conducted using mixed model for repeated measures (MMRM). The percent change from baseline will be calculated and reported by exponentiating the estimates for the change from baseline in above model.

Analyses for percentages of participants reaching Lp(a) <125 nmol/L and <75 nmol/L at Day 60, 180, 240, 360, and 540 will be conducted using logistic regression modeling.

In these models, additional covariates may be added, if deemed necessary. The details will be provided in the SAP.

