4.1. General Considerations

Statistical analysis of this study will be the responsibility of Lilly or its designee. Some analyses and summaries described in this analysis plan may not be conducted if not warranted by data (for example, too few events to justify conducting an analysis). Additional analyses of the data may be conducted as deemed appropriate.

Unless otherwise noted, all tests will be conducted at a 2-sided alpha level of 0.05, and confidence intervals (CIs) will be calculated at 95%, 2-sided. All tests of interactions between treatment groups and other factors will be conducted at a 2-sided alpha level of 0.10.

Unless stated otherwise, statistical summaries and analyses will be conducted based on planned randomized treatment group (LY 16 mg 2 doses, LY 96 mg 2 doses, LY 400 mg 2 doses, 400 mg 1 dose plus placebo 1 dose, and placebo 2 doses), regardless of the actual treatment(s) received by the participant. Assessment at or before Day 180 will pool data from both treatment arms assigned to the 400-mg dose.

The primary efficacy assessment, guided by the "treatment-regimen" estimand, which represents the efficacy regardless of treatment discontinuation, will be conducted using the full analysis set (FAS) (Section 3). A restricted maximum likelihood-based, mixed-effect model repeated measures (MMRM) analysis will be used to analyze continuous longitudinal variables. All the longitudinal observations at each scheduled postbaseline visit will be included in the analysis. The model for primary efficacy endpoint of percent change from baseline in Lp(a) will include log(Lp[a])-log(Baseline of Lp[a]) as the dependent variable and the fixed class effects of treatment group (LY 16 mg 2 doses, LY 96 mg 2 doses, LY 400 mg 2 doses, LY 400 mg 1 dose and placebo 1 dose, placebo 2 doses), strata (high risk of cardiovascular events for Lp[a] analysis; high risk of cardiovascular events and Lp[a] strata for non-Lp[a] biomarkers analyses), visit, and treatment-by-visit interaction, as well as the continuous, fixed covariate of baseline Lp(a). An unstructured covariance structure will be used to model the within-participant errors. Significance tests will be based on least squares (LS) means and Type III tests. SAS PROC MIXED will be used to perform the analysis. If this analysis fails to converge, the following covariance structures will be tested in order:

- 1. Toeplitz with heterogeneity
- 2. autoregressive with heterogeneity

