- 3. compound symmetry with heterogeneous variances
- 4. Toeplitz
- 5. autoregressive, and
- 6. compound symmetry without heterogeneous variances.

The first covariance structure that converges will be used. The Kenward-Roger approximation will be used to estimate denominator degrees of freedom. Comparisons of difference in time-averaged response from baseline for each treatment group of LY3819469 versus placebo reference group will be made by using contrasts of LS means.

Unless specified otherwise, safety assessments will be guided by an estimand comparing safety of LY3819469 doses with placebo irrespective of adherence to intervention. Thus, safety analyses will be conducted using the FAS (Section 3).

Baseline is defined as the last nonmissing measurement recorded on or before the randomization visit, prior to the first dose of intervention, unless otherwise specified. Data may exist at visits where the variable was not scheduled to be collected. In these situations, data from the early discontinuation visit that does not correspond to the planned collection schedule will be excluded from the MMRM, analysis of covariance (ANCOVA), or logistic regression analysis.

Multiple imputation will be used to impute corresponding missing potential outcome according to the missingness pattern. Table EZEB.4.2 summarizes the strategy to handle ICEs and the imputation method to handle missing values for efficacy endpoints.

For continuous measures, summary statistics will include sample size, mean, standard deviation (SD), median, minimum, and maximum for the actual, the change from baseline and percent change from baseline measurements. LS means and standard errors derived from the analysis (MMRM or ANCOVA) models will also be displayed for the change from baseline measurements. Treatment comparisons will be displayed showing the treatment difference LS means and the 95% CIs for the treatment differences, along with the p-values for the treatment comparisons. For categorical measures, summary statistics will include sample size, frequency, and percentages. A logistic regression model will be used to examine the treatment difference in binary efficacy outcomes with missing endpoints imputed. Fisher's exact test or Pearson's chi-square test will be used for treatment comparisons in other categorical outcomes.

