4.4.2. Main Analytical Approach

The time-averaged endpoints will be analyzed using the MMRM in a manner similar to method in Section 4.3.2 for the "efficacy estimand" as described in Section 1.1.

The following 2 study objectives will be analyzed using MMRM and the associated efficacy estimand:

- percent change from baseline and absolute change from baseline to Days 60, 180, 240, 360, and 540 for
 - o Lp(a)
 - o ApoB, and
 - o hsCRP
- percent change from baseline and absolute change from baseline in
 - o LDL-C
 - o total cholesterol
 - HDL-C, and
 - o TG.

Binary endpoints with missing values imputed by categorizing (Yes, No) the imputed values for the corresponding continuous endpoints as described in Table EZEB.4.2 will be analyzed using a logistic regression model with treatment and high-risk cardiovascular disease strata as fixed effects and the continuous baseline value as a covariate.

Table EZEB.4.5 summarizes the objective, endpoints, analysis approaches, and additional information for the efficacy estimand analyses.

	Relative to the Efficacy	Analysis Conducted in a	
Objectives	Measure	Manner Similar to	Additional Information
To evaluate if	Percent change from	MMRM model in	
LY3819469 is superior to	baseline in time-averaged	Section 4.3.2	
placebo in percent Lp(a)	Lp(a) over		
reduction over	 Days 60-180 		
• Days 60-180	• Days 240-360		
• Days 240-360	• Days 30-180, and		
• Days 30-180,	• Days 30-360		
and			
• Days 30-360			
Compare the effect of	Percent change from	MMRM model described	The continuous clinical
LY3819469 to placebo on	baseline and absolute	in Section 4.4.2	measures, including
cardiovascular biomarkers	change from baseline to		Lp(a), ApoB, and
	Days 60, 180, 240, 360,		hsCRP, may be log
	and 540 for		transformed before
	• Lp(a)		statistical analyses.
	• ApoB		LSM estimates will be
	• hsCRP		plotted by treatment
			through Day 540.
Compare the lipid profile	Percent change from	MMRM model described	The lipid biomarkers
in response to	baseline and absolute	in Section 4.4.2	may be log transformed
LY3819469 versus	change from baseline in		before statistical
placebo	lipid profile		analyses.
	• LDL-C		

 Table EZEB.4.5.
 Efficacy Estimand Analysis

	Relative to the Efficacy	Analysis Conducted in a	
Objectives	Measure	Manner Similar to	Additional Information

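### Lp(a), ApoB, hsCRP and lipids are measured twice before dosing but the efficacy models use only the last value: a modest loss of precision, not an error

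*SAP*

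**What the plan says.** Protocol 1.3 (schedule of activities) marks Lp(a), ApoB, hsCRP and the lipid panel at both Visit 1 and Visit 2; the lipid row, for example, opens "Lipid panel Х Х". For Lp(a) the text says that "central laboratory testing for Lp(a) is still required as part of the screening procedures conducted at Visit 1", whatever the prescreening result was. Visit 1 falls at most 21 days before randomization (Protocol 10.7 allows up to 45 days in exceptional circumstances). Both visits are fasting (Protocol 5.3.1). Both are pre-dose: "All procedures (screening and baseline) need to be completed prior to the first dose of study intervention". Background lipid-lowering and hormone therapy "must be on a stable regimen for at least 4 weeks prior to Visit 1" (Protocol 5.1), so both samples should fall under the same regimen.

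SAP 4.1 then defines one value: "Baseline is defined as the last nonmissing measurement recorded on or before the randomization visit, prior to the first dose of intervention". Protocol 9.3.1 has the same rule. The MMRM in SAP 4.1 has a single continuous baseline term, and the logistic models in SAP 4.4.2 use "the continuous baseline value as a covariate". No efficacy model uses Visit 1 when Visit 2 is present. Protocol 9.3.3 leaves room for more: "In these models, additional covariates may be added, if deemed necessary", with details left to the SAP; Protocol 9.3.2 has a similar provision for the primary model.

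**The concern.** A single baseline measurement carries assay and biological noise. Adjusting for it leaves unexplained some of the stable between-person difference that a second pre-dose measurement would help to capture. The second measurement is already in the database, and because it precedes randomization, adjusting for it does not bias the treatment contrast.

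Precision matters more for some endpoints than for others. The stated power covers only the primary Lp(a) endpoint (SAP 5). ApoB and hsCRP are secondary and the lipid profile is exploratory; none has a stated power or target effect. Their comparisons rest on about 24 completers on 16 mg and 48 in each other arm, with the two 400-mg arms pooled to about 96 through Day 180.

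**Working it through.** **The plan's own figure.** One allocation share is 254/9 = 28.2. Completers are 28.2 × 0.85 = 24.0 for 16 mg and 56.4 × 0.85 = 48.0 for each other arm, as stated. With SD 20 and a difference of 70 points:

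- 24 vs 48: SE = 20 × √(1/24 + 1/48) = 5.0, and 70/5.0 = 14 SEs.
- 48 vs 48: SE = 20 × √(2/48) = 4.1, about 17 SEs.
- 96 vs 48: SE = 20 × √(1/96 + 1/48) = 3.5, about 20 SEs.

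Power is about 1.000 in each case, so the stated figure of above 99% reproduces.

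**Single-visit markers (ApoB, hsCRP, lipids), equal correlation.** Let ρ be the correlation between any two visits. The documents give no value, so ρ is an assumption. As a share of the outcome variance, the residual is

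- one baseline: 1 − ρ²
- two baselines: 1 − 2ρ²/(1 + ρ)
- ratio: (1 + 2ρ)/(1 + ρ)²

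| ρ (assumed) | Variance ratio | Variance cut | SE cut |
|---|---|---|---|
| 0.3 | 1.6/1.69 = 0.947 | 5% | 3% |
| 0.4 | 1.8/1.96 = 0.918 | 8% | 4% |
| 0.5 | 2.0/2.25 = 0.889 | 11% | 6% |
| 0.6 | 2.2/2.56 = 0.859 | 14% | 7% |
| 0.7 | 2.4/2.89 = 0.830 | 17% | 9% |
| 0.8 | 2.6/3.24 = 0.802 | 20% | 10% |

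A simulation of 48 vs 48 (8,000 runs) gave ratios of 0.861 at ρ = 0.6 and 0.819 at ρ = 0.7, in line with the formula.

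**Unequal correlation.** Write r1 and r2 for the correlations of Visits 1 and 2 with follow-up, and c for the correlation between them. With both values as covariates, R² = (r1² + r2² − 2·r1·r2·c)/(1 − c²).

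- c = 0.7, r1 = r2 = 0.6: R² rises from 0.36 to (0.72 − 0.504)/0.51 = 0.4235. The residual goes from 0.64 to 0.577, ratio 0.901: a cut of about 10%.
- c = 0.6, r1 = 0.4, r2 = 0.6: R² = (0.52 − 0.288)/0.64 = 0.3625. The residual is 0.6375 against 0.64, ratio 0.996: no useful gain. Here the simple mean of the two values gives R² = 0.5²/0.8 = 0.3125, residual 0.6875, ratio 1.07: a loss. This is why the values should enter separately.

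**Primary Lp(a) contrast.** The trapezoidal weights for Days 60, 120 and 180 are 0.25, 0.5 and 0.25, with sum of squares 0.375. An SD of 20 points around a 70% fall is about 0.20/0.30 = 0.67 on the log scale for the active arms; 0.20 is used for placebo. Assumed: log SD 0.35 for the true baseline level and within-person CV 5% to 15%. The log-change variance in each arm is held at 0.67² or 0.20².

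Worked case, CV 10%, 16 mg vs placebo. The residual variance falls from 0.4437 to 0.4392 (active) and from 0.0393 to 0.0348 (placebo). The contrast variance goes from 0.4437/24 + 0.0393/48 = 0.01931 to 0.4392/24 + 0.0348/48 = 0.01903, ratio 0.986.

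| Assumed CV | 24 vs 48 | 48 vs 48 | 96 vs 48 |
|---|---|---|---|
| 5% | 0.996 | 0.995 | 0.993 |
| 10% | 0.986 | 0.982 | 0.974 |
| 15% | 0.972 | 0.964 | 0.949 |

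The variance cut is about 0.4% to 5%. It is small because the spread in response between participants dominates.

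**Cost.** One extra covariate costs roughly 1/96, or about 1% of variance, at 48 vs 48.

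**The case against.** The strongest reply is that nothing here is wrong. A last-value baseline is standard, unbiased and stated alike in both documents. The protocol's wording on further covariates is permissive, and the SAP made its choice: cardiovascular-risk stratum and baseline, plus the Lp(a) stratum for other markers. All of that stands. A reader might infer that the SAP omitted something promised, or that the treatment contrasts are biased; the documents support neither.

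The reply also limits the size, rightly. Every correlation is assumed. A reader might put ρ = 0.95 into the formula and claim a 24% variance cut, worth 31% more participants, but no document supports such a value for ApoB, hsCRP or lipids. The only marker described as having low within-person variability is Lp(a) (Protocol 2.2.1), where the gain is not needed. Nor does the formula show that these markers benefit most: its proportional gain rises with ρ, so taken alone it favors the most stable marker. The small Lp(a) gain comes from the response spread, a separate argument.

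Finally, Visit 1 may be the poorer predictor. Exclusion 13 (Protocol 5.2) admits an infection under treatment at Visit 1 if therapy ends before Visit 2, which could inflate that hsCRP value. This weakens the gain but does not bias the contrast, and entering the values separately lets the model give Visit 1 little weight.

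**Conclusion.** The point holds as a modest efficiency gain, not as a defect. For ApoB, hsCRP and lipids the variance cut is about 5% to 20% if visits correlate equally at 0.3 to 0.8, about 10% in the 0.7/0.6 case, and near zero, possibly not repaying the degree of freedom, if Visit 1 is clearly the weaker predictor. For the primary Lp(a) contrast the cut is about 0.4% to 5% under the plan's SD and an assumed CV of 5% to 15%. It would be larger if response varied less between participants than that SD implies, but the primary conclusion does not depend on it.

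A reader might infer that the biomarker comparisons fail without this change. The documents give no target effect or variability for those markers, so that cannot be shown.

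**What to change.** Set the following in the SAP before unblinding:

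- Keep the last pre-dose value (normally Visit 2) for the change score and the reported percent change.
- In the ApoB, hsCRP and lipid MMRMs, add the Visit 1 value of the same analyte as a second continuous covariate, on the same scale as the existing baseline term. This is optional for the Lp(a) models.
- Do not average the two values. Besides the possible loss of precision, Lp(a) is selected at 175 nmol/L or more at Visit 1, so averaging would slightly raise the reported Lp(a) baseline.
- If Visit 1 is missing, use the Visit 2 value.
- Keep the single-baseline model as a sensitivity analysis.

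The cost is a short SAP addition and one degree of freedom per model, with no new sampling. The downside is little or no gain where Visit 1 predicts poorly.

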1.1. Objectives, Endpoints, and Estimands

Endpoints	
 Percent change from baseline in time- averaged Lp(a) over Days 60-180 	
 Percent change from baseline in time-averaged Lp(a) over Days 240-360, Days 30-180, and Days 30-360 Proportion of participants achieving Lp(a) <125 and <75 nmol/L at Days 60, 180, 240, 360, and 540 Percent change from baseline and absolute change from baseline to Days 60, 180, 240, 360, and 540 for Lp(a) ApoB bsCRP 	
Population PK parameters	
· · · ·	
 Absolute change from baseline in Lp(a) at Days 60, 180, 240, 360, and 540 Proportion of participants achieving Lp(a) lowering of at least 150 nmol/L at Days 60, 180, 240, 360, and 540 	
 Percent change from baseline and absolute change from baseline for lipid profile LDL-C total cholesterol HDL-C triglycerides Incidence of treatment-emergent ADAs 	

Abbreviations: ADA = antidrug antibody; ApoB = apolipoprotein B; HDL-C = high-density lipoprotein-cholesterol; hsCRP = high-sensitivity C-reactive protein; LDL-C = low-density lipoprotein-cholesterol;

Lp(a) = lipoprotein(a); PK = pharmacokinetics.

Primary estimand

The primary clinical question of interest is: What is the intervention difference in percent change from baseline in time-averaged lipoprotein(a) (Lp[a]) over Days 60 to 180 of study intervention in participants who meet the inclusion criteria regardless of treatment discontinuation or initiation of excluded medications and Lp(a) modifying medication for any reason?

The primary estimand characterizes the treatment effect regardless of intercurrent events (ICEs) and is named the "treatment-regimen estimand."

CONFIDENTIAL

The treatment-regimen estimand is described by the following attributes:

- Population: participants who meet the enrollment criteria. Further details can be found in Section 5 and Section 9 of the study protocol EZEB.
- Endpoint: percent change from baseline in time-averaged Lp(a) over Days 60 to 180, which will be calculated by area under the curve (AUC) between Day 60 to Day 180 divided by 120.
- Treatment condition: the randomized treatment. Further details on study interventions, and concomitant interventions can be found in Section 6 of the study protocol EZEB.

There are no ICEs, because treatment discontinuation and initiation of medications that are known to impact Lp(a) level are part of the treatment condition.

Population-level summary: percent change from baseline in time-averaged Lp(a) over Days 60 to 180.

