For Lp(a), only nmol/L will be reported because there is no direct conversion to conventional (CN) units. For other laboratory values, both CN and the International System of Units (SI) units will be presented.

Endpoints that compare treatment groups based on percent change from baseline will be conducted by log-transformation of the dependent variables. Standard errors and 95% CIs will be constructed using the delta method. The LS means and standard error for each treatment, difference in LS means between arms, and corresponding 95% CIs will be calculated as shown in Table EZEB.4.1, where Z_b is the baseline of the log of the response.

Table EZEB.4.1.	Summary of Reported Quantities for Variables Requiring Log-
	Transformation

Quantity		Change from Baseline	Percent Change from Baseline	
Within Treatment	Estimate	$\left[\exp\left(\hat{\mu}_{\Delta \mathbf{Z},k}\right) - 1\right]\exp(\bar{Z}_{b})$	$\left[\exp(\hat{\mu}_{\Delta \mathrm{Z},k})-1 ight] imes 100$	
	SE	$\exp(ar{Z}_{b\cdot})\exp(\hat{\mu}_{\Delta Z,k})\cdot\widehat{SE}_{\Delta Z,k}$	$\exp(\hat{\mu}_{\Delta Z,k}) \cdot \widehat{SE}_{\Delta Z,k} imes 100$	
	p-value	NR	p_k	
	Estimate	$[\exp(\hat{\mu}_{\Delta Z,k}) - \exp(\hat{\mu}_{\Delta Z,R})] \cdot \exp(\bar{Z}_{b})$	$(\exp(\hat{\mu}_{\Delta Z,k \ vs \ R}) - 1) \times 100$	

Quantity		Change from Baseline	Percent Change from Baseline	
Between- Treatment Difference (Treatmen	SE	$e^{\bar{Z}_{b}}\sqrt{e^{2\hat{\mu}_{\Delta Z,k}}\cdot\left(\widehat{SE}_{\Delta Z,k}\right)^{2}+e^{2\hat{\mu}_{\Delta Z,R}}\cdot\left(\widehat{SE}_{\Delta Z,R}\right)}$	$\exp(\hat{\mu}_{\Delta Z,k\ vs\ R})\cdot\widehat{SE}_{\Delta Z,k\ vs\ R}\times 100$	
Reference	p-value	NR	$p_{\Delta Z,k \ vs \ R}$	
Ailii)	95% CI	Estimate $\pm \Phi^{-1}(1-\frac{\alpha}{2})$ *SE	$([\exp(L_{\Delta Z,k vs R}) - 1] \times 100, [\exp(U_{\Delta Z,k vs R}) - 1] \times 100)$	

Abbreviations: CI = confidence interval; NR = not reported; SE = standard error.

In general, a time-averaged parameter will refer to the AUC constructed using the trapezoidal rule, applied to the parameter according to the scheduled time, divided by the length of observation. For example, a time-averaged dependent variable for Days 60 to 180 will equal *AUC*/120, where *AUC* represents the AUC constructed by the trapezoidal rule.

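### The between-arm SE for absolute change in SAP Table EZEB.4.1 omits the covariance of the two LS means, so its 95% CI is usually somewhat too wide

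*SAP*

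**What the plan says.** SAP Section 4.1 sets one rule for log-transformed variables: "Standard errors and 95% CIs will be constructed using the delta method". It adds that the "difference in LS means between arms, and corresponding 95% CIs will be calculated as shown in Table EZEB.4.1". Table EZEB.4.1 then gives two columns for the between-treatment comparison.

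- **Percent change.** The SE is exp of the k-versus-R contrast times the SE of that contrast, ending in "SE}_{\Delta Z,k\ vs\ R}\times 100". The CI exponentiates the contrast's own limits.
- **Absolute change.** The estimate is `[exp(mu_k) − exp(mu_R)] × exp(Zb)`. The SE is exp(Zb) times the root of a sum of two within-arm terms. The last legible part is "e^{2\hat{\mu}_{\Delta Z,R}}\cdot\left(\widehat{SE}_{\Delta Z,R". The CI is the estimate plus or minus the normal quantile times this SE, and the p-value is marked as not reported.

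Both LS means come from one MMRM. Its class effects include cardiovascular risk for Lp(a), and for other markers "high risk of cardiovascular events and Lp[a] strata for non-Lp[a] biomarkers analyses". It also has a shared baseline term: "as well as the continuous, fixed covariate of baseline Lp(a". Section 4.1 adds: "Significance tests will be based on least squares (LS) means and Type III tests". I found no statement of how LS means are weighted over strata.

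The absolute-change column serves listed endpoints. SAP Section 1.1 has "Percent change from baseline and absolute change from baseline to Days 60, 180, 240, 360, and 540 for" Lp(a), ApoB and hsCRP.

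**The concern.** The delta method applied to a difference of two exponentials needs the joint covariance matrix of the two estimates. The absolute-change cell uses only the diagonal. Two LS means from one model share the estimated stratum and baseline coefficients, and so share part of their error. A shared error largely cancels in a difference. A formula that ignores the sharing counts it twice.

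The column reports no p-value, so the CI is the only inference given for absolute change. The two columns would also describe one comparison from one fit with different precision, for no scientific reason. The effect is potentially larger for a marker that treatment barely moves than for Lp(a), because the omitted term is scaled by `exp(mu_k + mu_R)`.

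**Working it through.** **Inputs from the documents.** 254 randomized in the ratio 1:2:2:2:2, with 15% dropout (SAP Section 5). The two 400-mg arms are pooled up to Day 180 (SAP Section 4.1).

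**The plan's own figures.** Table EZEB.4.1 gives no numerical SE. The nearby figures reproduce:
- Completers: 254 × 1/9 × 0.85 = 23.99 and 254 × 2/9 × 0.85 = 47.98, against the stated 24 and 48.
- Power for the smallest comparison: 0.70 / (0.20 × √(1/24 + 1/48)) = 0.70 / 0.05 = 14 standard errors, so power exceeds 99% as stated.

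**Assumptions (not in the documents).** Stratum prevalence p, shown as a range and equal in all arms; LS means weighting the strata equally; one visit standing in for the MMRM; baseline covariate left out. Completers are 24, 48, 96 (pooled 400 mg) and 48 (placebo), N = 216. The residual SD and exp(Zb) cancel in the ratio.

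**Formulas, with residual variance 1 and one stratum factor:**
- `C = Cov(LSmean_k, LSmean_R) = (0.5 − p)² / [p(1 − p)N]`
- `V_k = 1/n_k + C` and `V_R = 1/48 + C`
- Table SE² = `a²V_k + V_R`, with `a = exp(mu_k)` and `exp(mu_R) = 1`
- Full delta-method SE² = `a²V_k + V_R − 2aC`

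**Worked case, 96 mg versus placebo at 80/20.**
- C = 0.09 / (0.16 × 216) = 0.002604, so V_k = V_R = 0.020833 + 0.002604 = 0.023438.
- No effect (a = 1): 0.046875 against 0.041667; ratio √1.125 = 1.061.
- 70% reduction (a = 0.3): 1.09 × 0.023438 = 0.025547, against 0.025547 − 0.6 × 0.002604 = 0.023984; ratio 1.032.

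**Table SE divided by full delta-method SE:**

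| Split | C | 16 mg, no effect | 96 mg, no effect | 400 mg pooled, no effect | Any dose, 70% reduction |
|---|---|---|---|---|---|
| 50/50 | 0 | 1.00 | 1.00 | 1.00 | 1.00 |
| 70/30 | 0.00088 | 1.014 | 1.021 | 1.028 | 1.01 |
| 80/20 | 0.00260 | 1.041 | 1.061 | 1.080 | 1.03 |
| 90/10 | 0.00823 | 1.124 | 1.181 | 1.236 | 1.08–1.09 |

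After Day 180 the 400-mg arms are separate, with 48 completers each. The 96-mg column then applies to them, and the upper end at 90/10 is 18%, not 24%. With a 95% reduction (96 mg) the ratio is only 1.011 at 87.5% prevalence.

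**Two stratum factors (the non-Lp(a) model).** If the factors are independent, their C values add. At 80/20 and 70/30, C = 0.00260 + 0.00088 = 0.00349. With no effect the ratio is √(1 + 2 × 0.00349/0.0625) = 1.05 for 16 mg and √(1 + 2 × 0.00349/0.03125) = 1.11 for pooled 400 mg.

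**Direction.** With unequal prevalences, C is proportional to `(0.5 − p_k)(0.5 − p_R)`. At 70% in the 96-mg arm and 30% on placebo it is negative, and the ratio is about 0.98 with no effect and 0.99 with a 70% reduction. With LS means at observed margins and equal prevalence, C is zero and the ratio is 1.00.

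**Baseline covariate.** Adding a simulated baseline covariate, 96 mg versus placebo at 80% prevalence, gives mean ratios of 1.056 (no effect) and 1.030 (70% reduction), close to 1.061 and 1.032 without it.

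**The case against.** The strongest reply is that the direction and size rest on an LS-mean weighting that the SAP does not state. That stands: every ratio above 1 in the table assumes equal weights, and with observed margins and equal prevalence the formula loses nothing. It does not make the formula correct, because the full delta-method SE holds under any weighting and the SAP itself calls for the delta method.

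A reader might infer that the SE is too large whenever a stratum is unbalanced. The documents do not support that. The sign follows the covariance, which turns negative when the two arms lie on opposite sides of 50%. Stratified randomization makes that unlikely once the strata are clearly uneven. With random 15% dropout, a 70% reduction and the stratum factor only, the table SE was too small in 34% of simulated trials at 50% prevalence, 3% at 55% and none at 60% or more. With a baseline covariate the shares were 58%, 29% and 4%.

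A reader might also infer that the excess depends only on the stratum mix. It does not: it shrinks as the Lp(a) reduction grows.

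Three further limits stand:
- The extracted formula is damaged at its right edge. The square on the last SE is lost, and I read the expression as the symmetric sum. The lost square is not an error in the plan.
- SAP Table EZEB.4.5 leaves log transformation optional, so ApoB and hsCRP are affected only if they are logged.
- Absolute change in Lp(a) is exploratory in Protocol Section 3, no p-value or decision rule uses this SE, and the expected error is conservative.

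**Conclusion.** The point holds as an omitted covariance term, and it is minor. As legible, the absolute-change SE in Table EZEB.4.1 departs from the SAP's own delta-method rule and from the percent-change column beside it. The SE and CI are too wide when the covariance is positive, as expected under stratified randomization with strata away from 50/50 and equally weighted LS means. They are about right with observed-margin weights and equal prevalence, and can be slightly too narrow if the arms straddle 50%.

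For Lp(a) at the stated 70% reduction the excess stays at about 3% or less up to an 80/20 split and reaches 8–9% at 90/10. The double-digit figures need a near-null effect together with either a 90/10 split or two uneven strata. The 24% figure also needs the pooled 400-mg arms, so it cannot arise after Day 180. A reader might take this as a threat to the primary result; it is not, because the primary and percent-change analyses use the contrast SE.

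**What to change.** In the absolute-change cell of Table EZEB.4.1, subtract `2 × exp(mu_k + mu_R) × Cov(LSmean_k, LSmean_R)` under the square root. Equivalently, apply the delta method to the joint covariance matrix of the LS means. State in Section 4.1 whether LS means weight strata equally or by observed margins. Section 4.1 and Table EZEB.4.2 also mention multiple imputation; if it is used for these endpoints, the covariance must be pooled across imputations along with the variances.

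The cost is one formula, one sentence and minor programming. Design, data collection and the primary analysis do not change.
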